Cost Measurement. Costs to be collected can be grouped into three broad categories: intervention delivery costs, participant time costs, and health care costs. Intervention costs incurred to develop both interventions will be excluded from the analysis as these costs have already been incurred and are thus “sunk” costs. Intervention Delivery Costs for both conditions will be estimated using both standardized estimates and convenience sampling of support staff and our interventionists. The time it takes to prepare for and execute CBT for SUD is specified in the treatment manual but will be assessed through a data tracking system, surveys, and counselor records to validate these estimates. Similar methods will be used to estimate time spent in identifying veterans with AUD, contacting veterans, and training veterans on the use of the mCM smart phone app. To reduce burden, we will not measure every activity for every subject for every occasion. Instead we will collect a convenience sample of observations toward the beginning and the end of the study to account for the fact that there may be a learning curve effect. The size of the convenience sample will depend on the variability we observe in the activity times—the larger the variability the larger the sample we will collect. In addition to labor costs, materials costs, including the cost of the mCM will be included.

Participant Time Costs (i.e., the opportunity costs to participants). This will include the time spent by participants in using the intervention strategies, techniques, or information. As part of the end-of-treatment follow-up, time spent on the intervention materials other than that involved in the treatment sessions will be assessed. In the intervention arm, the number of videos submitted will be used to assess the time involved in providing bioverification as part of mCM. We will derive participant time cost estimates for each group by combining the time estimates with standard wage estimates adjusted for age, gender, and if possible race, derived from the Statistical Abstract of the United States. Because we chose to conduct the cost-effectiveness analysis from the societal perspective, the use of mean wage rates has higher generalizability and validity than self-reported wages by the subjects. *Health care costs* will be obtained from VA medical records for outpatient, inpatient and medication use one year prior to trial enrollment and through the final follow-up.

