Alcohol Readiness to Change	Participant	X		X	X	
Alcohol Purchase Task	Study staff	X		X	X	X
Drinking Norms Rating Form	Participant	X		X	X	X
Alcohol Use, Short Form (PROMIS)	Participant	X		X	X	X
Alcohol Use, Positive Expectancy (PROMIS)	Participant	X		X	X	X
Alcohol Use, Positive Consequences (PROMIS)	Participant	X		X	X	X
Alcohol Use, Negative Expectancy (PROMIS)	Participant	X		X	X	X
Drinking Motives Questionnaire	Participant	X		X	X	X

Alcohol Risk Beliefs	Participant	X		X	X	
Sociodemographic, Clinical, and Process Variables						
Sociodemographic and Military	Participant	X				
DRRI Combat Experiences Scale	Participant	X				
Beck Scale for Suicidal Ideation	Participant	X		X	X	X
Insomnia Severity Index	Participant	X		X	X	X
Dimensions of Anger Reactions	Participant	X		X	X	X
Smoking Exposure Questionnaire	Participant	X		X	X	X
Barratt Impulsivity Scale	Participant	X		X	X	X
Delay Discounting	Participant	X		X	X	X
MOS Social Support	Participant	X		X	X	X
Medical Problems Checklist	Participant	X			X	X
Medications Checklist	Participant	X			X	X
Individual Treatment Alliance	Participant			X		
Working Alliance Inventory	Participant		X*			
Qualitative Interview	Study staff			X		
Satisfaction/Acceptability	Participant			X		
Alcohol Outcome Measures						
Timeline Follow-Back	Study staff	X		X	X	X
Heavy Drinking Days	Study staff	X		X	X	X
% Days Drinking	Study staff	X		X	X	X
Binge Drinking Episodes	Study staff	X		X	X	X
PEth Testing (bioverification)	Study staff				X	X
Addiction Severity Index	Participant	X		X	X	X
Quality of Life, Healthcare Utilization, and Cost Measurement						
EuroQol	Participant	X	X**	X	X	X
Insurance Question	Participant	X				
WHOQOL-BREF	Participant	X		X	X	X
Cost Measurement	Statistical team			X		
Self-Report Healthcare Utilization Measure	Participant	X		X	X	X
Healthcare Utilization	Statistical team	X		X	X	X

* given at CBT sessions 1, 7, and 12 only; ** given at CBT session 7 only

D.8.4. Socio-demographic Measures. Sociodemographic variables will be collected. Social support will be assessed with the MOS social support scale. Impulsivity will be assessed via self-report and through a delay-discounting task (Richards, Zhang, Mitchell, & DeWit, 1999; Garcia-Rodriguez, Secades-Villa, Weidberg, & Yoon, 2013).

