Aim 3: To examine the hypothesis that incentivizing long-term abstinence will increase AUD aftercare treatment utilization, enrollment in VA and/or non-VA alcohol treatment programs will be determined both in the first 6 months following randomization and the second 6 months leading up to the 12-month follow-up. Logistic MLM will be used to model treatment utilization during each of these intervals as a function of randomization to the long-term abstinence incentive, time, and the interaction between group and time. Randomization to CM will be covaried. Linear contrasts will be specified at each time point to examine the hypothesis that long-term incentives to promote abstinence will result in greater likelihood of AUD treatment utilization both prior to and following the 6-month incentive. To examine the hypothesis that long-term abstinence incentives will be associated with higher rates of self-reported abstinence and fewer heavy drinking days at 6 and 12 months, MLM analyses similar to those proposed for Aim 1 will be conducted. Specifically, logistic MLM will be used to model abstinence as a function of long-term incentive, time (categorized as end of treatment, 6 months, 12 months), and the interaction between incentive and time. Randomization to CM will be covaried. Linear contrasts will be specified at each time point to examine the hypothesis that a long-term incentive for abstinence will result in higher abstinence rates than no incentive at 6 and 12 months. A similar count-based model (e.g., Poisson, negative binomial) will be conducted to analyze number of days of heavy drinking (per 30

days). In addition to modeling the effects of long-term incentive, time, and the interaction between incentive and time, number of days of heavy drinking recorded at baseline and randomization to CM will be covaried. Linear contrasts will compare effects of the incentive at 6 and 12 months.

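### The Aim 3 utilization model has no term for earlier AUD treatment, although prior-year VA use is already extracted: some power is probably lost, by an amount the documents cannot fix, and there is no bias

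*Combined protocol and SAP*

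**What the plan says.** The Aim 3 paragraph of section F defines the outcome: "enrollment in VA and/or non-VA alcohol treatment programs will be determined both in the first 6 months following randomization", and again over the six months leading to the 12-month follow-up. The model statement reads: "Logistic MLM will be used to model treatment utilization during each of these intervals as a function of randomization to the long-term abstinence incentive". The other terms are time and its interaction with the incentive. One covariate is added: "Randomization to CM will be covaried". In the same paragraph, the heavy-drinking count model also adjusts for the starting value of its own outcome: "number of days of heavy drinking recorded at baseline and randomization to CM will be covaried".

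Use before the trial is collected in two ways. Section D.6 says that the cost data "will be obtained from VA medical records for outpatient, inpatient and medication use one year prior to trial enrollment and through the final follow-up". Table 3 (section D.8) schedules the "Self-Report Healthcare Utilization Measure" at screening as well as at the later assessments, and has a record-based utilization row at screening too. Section D.1 names the VA electronic record and participant report as the sources for aftercare use, so the VA part of the outcome and the prior-year extract share a source.

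The opening of section F allows for covariate adjustment if baseline differences appear, and for sensitivity analyses on baseline variables. The variables it lists for comparison are demographics, baseline drinking, and PTSD and depressive symptoms. Earlier treatment use is not among them. Randomization (D.3) is stratified only on comorbid non-tobacco SUD.

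**The concern.** Whether a person used AUD treatment in the past year is likely to be one of the better predictors of whether that person uses it in the next. Section D.2 excludes people now in professional behavioural AUD treatment and people with past medical alcohol detoxification. Other earlier treatment remains possible and can differ between participants. The design does not balance it and no model adjusts for it.

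At stake is the efficiency of the incentive contrast on a binary outcome in at most 140 people. The validity of the contrast is not in question. A clause that permits adjustment after an imbalance has been seen is also weaker than one covariate fixed in advance.

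**Working it through.** **The plan's own power figure.** Section F sizes the trial on the Aim 1 CM contrast. With m observations per person and ICC 0.20, the effective sample size is the sum of m/(1 + (m − 1) × 0.20).
- Complete data: 140 × 3/1.4 = 300.
- With attrition to 119, 101 and 86: 86 people have three observations, 101 − 86 = 15 have two, and 119 − 101 = 18 have one. This gives 86 × 3/1.4 + 15 × 2/1.2 + 18 = 184.3 + 25 + 18 = 227.3.
- At 113.5 per group and d = 0.43, power is 0.8996. Two-sided alpha 0.05 is assumed here, because the documents do not state it.

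The stated 300, 227 and 90% therefore reproduce. No power figure is given for Aim 3 utilization.

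**Inputs for the check.** From the documents: 140 participants (section A), hence about 70 per incentive level. Assumed, because the documents give no values: utilization of 30% without and 50% with the incentive, the prevalence of prior use, its odds ratio for later use, and no attrition.

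**Approximation.** Without the covariate, power = Φ[(0.20 − 1.96 × √(2 × 0.4 × 0.6/70)) / √((0.3 × 0.7 + 0.5 × 0.5)/70)] = Φ[(0.20 − 1.96 × 0.0828)/0.0811] = Φ(0.465) = 0.679. A baseline covariate with correlation ρ to the outcome acts roughly like raising N to 140/(1 − ρ²):

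| ρ | equivalent N | power | gain (points) |
|---|---|---|---|
| 0.1 | 141 | 0.683 | 0.4 |
| 0.2 | 146 | 0.697 | 1.8 |
| 0.3 | 154 | 0.720 | 4.1 |
| 0.4 | 167 | 0.755 | 7.6 |
| 0.5 | 187 | 0.801 | 12.2 |

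**Simulation.** One interval, logistic regression on incentive and CM, without and with a prior-use indicator, 6,000 replicates per row. The Monte Carlo standard error of each power is about √(0.68 × 0.32/6000) = 0.006.

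| prior users | odds ratio for later use | power without | power with | variance ratio, standardized risk difference |
|---|---|---|---|---|
| 10% | 2 | 0.671 | 0.679 | 0.994 |
| 20% | 2 | 0.679 | 0.687 | 0.989 |
| 20% | 4 | 0.673 | 0.710 | 0.933 |
| 20% | 8 | 0.675 | 0.748 | 0.863 |
| 40% | 4 | 0.679 | 0.729 | 0.899 |
| 40% | 8 | 0.676 | 0.774 | 0.804 |

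- Standard error of the log odds ratio (40%, odds ratio 4): it rises with adjustment, from 0.357 to 0.384. Power rises because the conditional log odds ratio grows by more.
- Type I error (no incentive effect, 30% prior users, odds ratio 4): 0.050 without and 0.049 with the covariate.
- Cost if prior use is unrelated to later use: the variance ratio is 1.007 to 1.010, about 1%.

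**Other assumed effects.** With overall use of about 35% and an incentive odds ratio of 3 (4,000 runs), power moves from 0.843 to 0.849 (10% prior users, odds ratio 2), from 0.784 to 0.831 (35%, 4) and from 0.667 to 0.763 (40%, 8). With an incentive odds ratio of only 1.5, the gains found were 0.1 to 2.3 points.

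**Chance imbalance.** The standard deviation of the between-arm difference in prior-use prevalence is √(2p(1 − p)/70): 0.073 at p = 0.25 and 0.083 at p = 0.40, or about 7 to 8 percentage points.

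**The case against.** The case for leaving the model alone has real substance.

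- **The spread of prior use may be small.** D.2 removes current behavioural treatment and past medical detoxification. D.4.2 asks participants not to start new AUD treatment during the treatment period, which takes up roughly half of the first six-month interval. Both restrictions make a gain near the lower end plausible. This stands.
- **The size is assumed throughout.** The simulation also treats one interval, whereas the plan has a two-interval multilevel model. This stands, and it is why the range must start at zero.
- **The omission is not unique.** The logistic abstinence models under Aims 1 and 3 also have no baseline term, so the utilization model follows the plan's other logistic models. The contrast with the count model is accurate but should not be read as a one-off slip.
- **Section F already allows adjustment.** It does so only conditionally, and earlier treatment use is not on its list. This answers the point only in part.
- **The covariate is not ready-made.** The extract is described for costing, no AUD-treatment indicator is defined from it, and the look-back period of the screening self-report is not stated. This stands and shapes the fix.

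A reader might also infer that chance imbalance in prior use contaminates the incentive effect. Under randomization such imbalance is random error, which the test and interval already allow for.

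**Conclusion.** The point holds as a small matter of efficiency. The Aim 3 utilization model leaves out a probable predictor that the trial could code from records it already plans to extract. The loss is one of power for the incentive contrast, or of precision for a standardized risk difference. The gain from adjustment is about zero if prior use is rare or weakly related to later use, and roughly 5 to 10 power points if it is common and strongly related. These figures rest on assumed rates, prevalences and associations, full follow-up and two-sided alpha 0.05.

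Two stronger readings are not supported. The unadjusted comparison is not biased. Nor is the standard error of the log odds ratio inflated by the omission, since adjustment increases it. Aim 3 is exploratory and the sample size rests on Aim 1, so the point is worth adopting but not essential.

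**What to change.** Before the incentive arms are compared, add to the SAP a covariate for any AUD treatment in the 12 months before enrolment, defined from the VA extract with the same codes as the VA part of the outcome. Add the screening self-report of non-VA use only if its look-back period allows an indicator over the same 12 months. Report a marginal (standardized) risk difference alongside the conditional odds ratio.

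The cost is a small coding task, an odds ratio that is now conditional on prior use and must be described as such, and about 1% in variance if the covariate proves unrelated to the outcome. No new data collection is needed for the VA-based version.

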Our long-term goal is to implement cost-effective treatments that reduce the morbidity and mortality associated with alcohol and substance misuse. VA has widely implemented evidence-based cognitive-behavioral therapy (CBT) for treatment of substance abuse disorders (Karlin & Cross, 2014). The primary goal of the current study is to evaluate the clinical effectiveness and cost effectiveness of CM as an adjunct to CBT for AUD. The trial will also explore the potential utility of a long-term abstinence incentive on treatment utilization and alcohol outcomes. We plan to conduct a comparative effectiveness trial with a 2 x 2 factorial design in which 140 veterans with AUD will be proactively recruited and randomized to receive either CM as an adjunct to state-of-the-art evidence-based CBT, or receive CBT alone; and to one of two long-term incentive conditions (i.e., receipt of a monetary incentive for abstinence/low-risk drinking at 6-months vs. no incentive). Specific aims include:

AIM 1: To evaluate the effectiveness of mobile contingency management, as an augment to evidence-based CBT for AUD, on (1) treatment engagement and retention, and (2) reduction in heavy drinking days and abstinence from alcohol at post-treatment, 6-month and 12-month follow-ups.

Hypothesis 1a: Mobile contingency management for AUD will be associated with greater treatment engagement and treatment completion.

Hypothesis 1b: Mobile contingency management for AUD will be associated with decreased self-reported heavy drinking days and increased rates of abstinence from alcohol at each follow-up.

AIM 2: To evaluate the cost effectiveness of CM as an adjunct to evidence-based CBT for SUD in quality adjusted life years (QALY).

Hypothesis 2: CM paired with CBT will result in greater cost-effectiveness compared to the CBT alone as measured by the incremental cost-effectiveness ratio.

AIM 3: To explore the effects of a long-term (six-month) abstinence incentive on (1) treatment utilization and (2) alcohol outcomes at the 6-month and 12-month follow-ups.

Hypothesis 3: A long-term abstinence incentive will (1) increase utilization of AUD aftercare and (2) be associated with reduced heavy drinking days and increased abstinence rates.

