As shown in Figure 3, proposed is a 2X2 factorial randomized clinical effectiveness trial testing the effects of combining CM as an adjunct to state-of-the-art, evidence-based CBT (CBT + CM vs. CBT only) and the effects of a single, long-term incentive for bioverified abstinence/no heavy drinking at 6-months follow-up (Long Term Incentive vs. No Incentive). All patients will be referred to standard aftercare and encouraged to participate in 12-step programs following the intervention. Use of aftercare and other health care utilization will be collected based on objective measures (VA electronic medical record) and participant report. Health-related quality of life will be collected at each follow-up. The primary endpoint (AIM 1) will be number of heavy drinking days in the past 30 days at the 6-month follow-up. Cost effectiveness analysis (AIM 2) will be performed using quality-adjusted life years (QALY) as the outcome. The utility of a long-term incentive (AIM 3) will be tested by examining use of aftercare and other alcohol-related treatment and heavy drinking days in the past 30 days at the 6 and 12-month follow-ups.

D.2. Patient Identification, Eligibility, and Recruitment

Patients will be identified from the Durham VA Health Care System (DVAHCS) using the hospital's computerized medical record. Records will be screened for AUD. After mailing introductory materials with an opt-out number, we will contact those who do not opt out via telephone to explain the study and recruit them for participation. If necessary, in order to reach female veterans, we can oversample women for the screening mailouts.

Figure 3. Trial Design

We will also utilize reactive recruitment methods as needed to reach potentially eligible veterans. For example, we will seek referrals from the DVAHCS Substance Use Disorders Clinic. In order to reach female veterans, we will seek referrals from the Women's Health Clinic. In addition, we will post IRB-approved flyers and brochures throughout the DVAHCS catchment area, especially in clinic areas and Vet Centers. In addition, we will post, if necessary, flyers and brochures in the community, in local restaurants, laundromats, university student centers, etc. We will also use online classified advertisements such as Craigslist.com to reach potential participants.

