Videos bioverifying alcohol abstinence will be reviewed by study staff to verify the participant's identity and alcohol abstinence. Study staff will write notes to the participant through the app to provide feedback on how the bioverification results translate into virtual scratch-off lottery tickets (scratch-offs). At that point, participants will use the app to reveal the scratch-offs and find out what level of reinforcement they have received. At the beginning of each session of CM+CBT, therapists will review the essential elements of CM as indicated on the Contingency Management Competence Scale (Petry, 2010). Essential elements include feedback and review of how bioverification results resulted in reinforcement draws, discussion of the mean number draws that could be earned if the participant is bioverified abstinent over the upcoming week, praise of the participant's efforts toward abstinence, communication of confidence that efforts will yield future success, and general competence ratings. This portion of the session will be rated by an independent fidelity rater using the Contingency Management Competence Scale. Therapists will be trained on the essential elements of CM during a half-day training. The CM portion of CM+CBT sessions will be videorecorded and rated by an independent fidelity rater.

Participants will be asked not to initiate any new treatments for AUD during the study treatment period. Following the active treatment period, participants will be encouraged to become involved with local 12-step programs and other aftercare.

D.4.3 Long Term Incentive

Participants randomized to the long-term incentive condition will receive \$300 for self-reported and bioverified 30-day abstinence from heavy drinking at the follow-up scheduled for 6-months after the initial quit date. Bioverification will be based on PEth test.

D.5. Rationale for CM Parameters

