D.8.7. Treatment Fidelity. Counselors will receive weekly supervision for CBT from [name] or another senior clinician. Following procedures recommended by the VA training program, we will utilize the Cognitive Behavioral Therapy for Substance Use Disorders Rating Scale to measure counselor adherence in delivering behavioral treatments for substance abuse disorders (Gnys, DeMarce, Raffa, & Karlin, 2014). A random selection of 10% of the counseling sessions will be rated for fidelity by rater who is otherwise independent of the conduct of the study. Fidelity ratings will be used in supervision to improve counseling. To measure therapeutic alliance, we will use the 16-item Individual Treatment Alliance Scale Revised Short Form, which has a demonstrated relationship with treatment dropout and treatment response in behavioral interventions (Pinsoff, Zinbarg, & Knobloch-Fedders, 2008). This measure will be given at the final treatment session for all participants, including participants who withdraw early from treatment.

D.8.8. Outcome Measurement and Biochemical Verification. At each treatment session, and at post-treatment and follow-ups, we will measure number of heavy drinking days (> 5 drinks in day for men, > 4 drinks in a day for women), binge drinking episodes (heavy drinking within a 2-hour period), number of drinking days, and drinks per drinking day. At follow-ups, we will conduct Timeline Follow-back interviews to improve self-reports of drinking behavior over the previous months. We will ask participants to complete items from the Addiction Severity Index (ASI) to assess the consequences of substance use on functioning in the previous month. Participants will complete all of the items of the Employment subscale, and items 1, 3, 7, 8, 9, 10, 28, 29, 30, 31, 32, and 34 of the Family/Social subscale. Early continuous abstinence will be defined as three consecutive weeks of alcohol abstinence in the first eight weeks after the quit attempt, a threshold that has been predictive of good long-term SUD outcomes (Carroll et al., 2014). We will bioverify self-reports of low risk drinking with fingerstick blood spot samples for PEth testing at 6-month and 12-month follow-ups.

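### Aim 3's 6-month heavy-drinking-day contrast uses the 30-day self-report that helps earn $300 in one incentive arm only, and Section F gives the scheduled PEth result no role in it

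*Combined protocol and SAP*

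**What the plan says.** **Payment.** D.4.3 (Long Term Incentive) pays $300 in the long-term incentive condition for "self-reported and bioverified 30-day abstinence from heavy drinking at the follow-up scheduled for 6-months after the initial quit date", with PEth as the verifying test. The payment table in D.9 confirms that only this condition is paid. Its row mentions bioverified abstinence and says nothing of self-report, so the self-report condition rests on D.4.3 alone.

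**Outcome.** D.1 tests the incentive on treatment use and on "heavy drinking days in the past 30 days at the 6 and 12-month follow-ups". D.8.8 obtains drinking data by participant report, with Timeline Follow-back interviews at follow-up. Section F, Aim 3 states the hypothesis that "long-term abstinence incentives will be associated with higher rates of self-reported abstinence and fewer heavy drinking days at 6 and 12 months". It plans a logistic multilevel model for abstinence and a count model for heavy drinking days. The count model covaries baseline heavy drinking days and CM assignment, and contrasts the incentive arms at 6 and 12 months.

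**Biomarker.** D.8.8 states: "We will bioverify self-reports of low risk drinking with fingerstick blood spot samples for PEth testing at 6-month and 12-month follow-ups". Table 3 lists PEth at the same two visits, with no baseline sample. Neither place limits it to one arm. Section F does not mention PEth or bioverification.

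**Status of the aim.** Section A introduces it as "AIM 3: To explore the effects of a long-term (six-month) abstinence incentive".

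**The concern.** The money depends on the randomized factor that Aim 3 evaluates. In one level of that factor, a participant with a heavy drinking day has a financial reason to report none; in the other level there is no such reason. Reporting behaviour could therefore differ by arm even if drinking does not, and the planned model cannot separate the two. The error would run in one direction only, towards fewer reported heavy drinking days in the paid arm, as Hypothesis 3 predicts.

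The trial will hold a biological check from both arms, but the plan does not say what happens in the analysis when that check contradicts a report. At stake is how the 6-month drinking result of Aim 3 is read. Self-reported abstinence at 6 months is exposed less directly, because D.4.3 pays for the absence of heavy drinking.

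**Working it through.** **1. The plan's own figures.** No figure is given for misreporting or for the power of Aim 3. The Section F calculation is for the CM hypothesis and reproduces: 140 × 0.85² = 101 at 6 months, and an effective sample size of 86×3/1.4 + 15×2/1.2 + 18 = 227. Only the 101 is used below (50.5 per incentive arm).

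**2. Passages side by side.**

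| Feature | Payment (D.4.3) | Aim 3 count outcome (D.1, D.8.8, F) |
|---|---|---|
| Behaviour | no heavy drinking | heavy drinking days |
| Window | 30 days | 30 days |
| Visit | 6 months | 6 and 12 months |
| Source | self-report and PEth | self-report |
| Arm | incentive only | both, contrasted |

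The documents do not name the instrument used for the payment decision. That it is the same report is a close inference from the shared behaviour, window and visit. A paid-arm participant who reports zero and fails PEth would lose the $300, yet as Section F is written would still contribute zero days.

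**3. Illustrative size. Every input except 101 and 140 is assumed.** Let m be the excess share of paid-arm participants with at least one heavy drinking day who report none, and k their true count relative to the average of such participants. With no true effect, the spurious rate ratio is 1 − m·k. Take 35% truly zero and positive counts of 1-30 with mean 8 or 12. At 50 per arm, the simulated standard error of the log ratio is 0.28 or 0.23 respectively. Then bias/SE = −ln(1 − m·k)/SE, and the favourable-tail error is approximately Φ(bias/SE − 1.96).

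| m | k | Ratio | Bias/SE | Favourable false positives |
|---|---|---|---|---|
| 0 | – | 1.00 | 0 | 2.5% |
| 0.05 | 0.5 | 0.975 | 0.09-0.11 | 3.1-3.2% |
| 0.05 | 1 | 0.95 | 0.18-0.22 | 3.8-4.1% |
| 0.10 | 0.5 | 0.95 | 0.18-0.22 | 3.8-4.1% |
| 0.10 | 1 | 0.90 | 0.38-0.46 | 5.7-6.7% |

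Simulation with an unadjusted t-test agrees. At m = 0.10 it gives about 6-7% for average drinkers and about 3.5-5% for lighter drinkers (ratio 0.95-0.96). At m = 0.05 it gives about 3-4.5%. With 20-50% truly zero, m = 0.10 and k = 1, the range is 4.9-7.8%. None of this simulates the planned baseline-adjusted multilevel count model.

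**4. What a PEth-confirmed outcome could show.** The 95% CI half-width for a difference in proportions is 1.96·√(2p(1−p)/n). At n = 50.5 this is 15.6, 18.6 and 19.5 points for p = 0.20, 0.35 and 0.50. At n = 56 (80% of 140, two arms) it is 14.8, 17.7 and 18.5. If PEth catches 50-80% of false reports, the extra discordant paid-arm participants at m = 0.10 number 50.5 × 0.65 × 0.10 × (0.5 to 0.8) = 1.6 to 2.6.

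**The case against.** The strongest reply is that PEth already polices the payment: a false report alone earns nothing, so denial pays only for someone who expects to pass the test. This stands in part. It weakens the motive, and it suggests that any deniers would be lighter drinkers, which is why the k = 0.5 rows deserve as much weight as k = 1. It does not close the gap, because PEth decides who is paid and not what enters the model.

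Second, Aim 3 is exploratory and the sample size rests on CM. That stands, and it limits the severity.

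Third, partial checks are already planned. No payment depends on the 12-month report, and aftercare use draws partly on VA records. Both reduce reliance on the 6-month drinking result, but neither resolves it.

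A reader might infer more than the documents support:
- *That participants are paid on their word.* D.4.3 requires PEth as well.
- *That PEth is collected only in the paid arm.* D.8.8 and Table 3 carry no such restriction; the gap is in the analysis plan.
- *That the primary CM comparison is biased.* The incentive is crossed with CM and covaried in the Aim 1 models, so that contrast is not materially affected.
- *That under-reporting will occur.* The documents contain no evidence of its presence or size.

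**Conclusion.** The point holds as a minor one. In one incentive arm, D.4.3 ties money partly to the self-report on which Section F contrasts the incentive arms at 6 months, and Section F gives the scheduled PEth result no role. Any excess under-reporting in the paid arm would favour Hypothesis 3.

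The plausible size is small to modest: under the stated assumptions, favourable false positives of roughly 3-7% against 2.5%, for 5-10% excess denial. These figures are illustrations; the conclusion rests on the text. It is confined to the 6-month drinking result of an exploratory aim. It gives no ground for dropping that contrast or for discounting the 12-month contrast, the utilization outcome or Aim 1.

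**What to change.** Keep the planned Aim 3 models and add the following to Section F.

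1. **One 6-month sensitivity analysis.** The outcome is zero self-reported heavy drinking days in the past 30 and a PEth result consistent with that report. Fix one analysis cut-off before data are seen and apply it identically in both incentive arms. Model by incentive arm, with CM assignment and baseline heavy drinking days covaried. Code anyone reporting a heavy drinking day as not confirmed, whatever the PEth result.
2. **Description of discordance.** Among those reporting no heavy drinking, give discordant and missing PEth by incentive arm, with the difference and its 95% CI, as description and not as a test.
3. **Missing PEth.** State which rule applies. D.10 treats missing data as relapse or heavy drinking, whereas Section F uses maximum likelihood and multiple imputation; the two need reconciling. One option is imputation that includes incentive arm, CM arm and same-visit self-report, since PEth has no baseline value, with missing = not confirmed as the alternative.
4. **Labelling.** Describe the planned 6-month result as an effect on self-reported drinking in all cases. Do not make the wording depend on discordance: with 50 per arm, 5% false discordance and 0-10% background denial in both arms (all assumed), the paid arm would show the higher discordant share by chance in about 31-49% of trials with no excess denial.
5. **Wording.** Reconcile the descriptions of what is verified: "receipt of a monetary incentive for abstinence/low-risk drinking at 6-months vs. no incentive" (Section A), "long-term incentive for bioverified abstinence/no heavy drinking at 6-months follow-up" (D.1), no heavy drinking (D.4.3), low-risk drinking (D.8.8) and abstinence (D.9).

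The cost is SAP text only, because the samples are already scheduled. The downsides are that the added estimate is imprecise (half-width about 15-20 points), PEth does not map exactly to a 30-day count, and the discordance table will be small.
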